6.12.3. Deaths, Other Serious Adverse Events, and Other Adverse Events for Review

TEAEs by Preferred Term will be reported.

The full summary of AEs is described in the CPMP SAP version 5.

6.12.4. Clinical Laboratory Evaluation

The general analysis of laboratory parameters is described in the CPMP SAP version 5.

In this ISA, laboratory results will be reported for the first 4-week, active-treatment period and separately for the entire 8-week study period.

Study BP02 will also consider the following analyses of laboratory analytes used to assess renal function. The planned summaries for these analytes are the same as those that have been described in the CPMP SAP. However, the reporting of these analytes will be separate from the general analysis of laboratory parameters.

Renal data analyses:

- Serum creatinine (change from baseline in mg/dL)
- Estimated glomerular filtration rate (eGFR; Chronic Kidney Disease Epidemiology Collaboration [CKD-EPI] algorithm using serum creatinine). Algorithm provided by the central laboratory.
- For eGFR calculation, we will summarize shift tables of eGFR changes for baseline versus postbaseline by minimum, maximum, and last observed eGFR result.
 - Category 1: Normal or increase in GFR (≥ 90 mL/min/1.73 m²)
 - Category 2: Mild reduction in GFR (60 to 89 mL/min/1.73 m²)
 - Category 3a: Moderate (a) reduction in GFR (45 to 59 mL/min/1.73 m²)
 - Category 3b: Moderate (b) reduction in GFR (30 to 44 mL/min/1.73 m²)

- Category 4: Severe reduction in GFR (15 to 29 mL/min/1.73 m²)
- Category 5: Kidney failure (GFR <15 mL/min/1.73 m² or dialysis)

Abnormal eGFR is specified below and will be summarized in the laboratory summary tables.

Abnormal low: <90 mL/min/1.73 m²

Abnormal high: as specified by the central laboratory.

6.12.5. Vital Signs and Other Physical Findings

The analysis of vital sign parameters is described in the CPMP SAP version 5.

Vital signs will be reported for the first 4-week, active-treatment period and separately for the entire 8-week study period.

6.12.6. Electrocardiograms

The analysis of ECG parameters is described in the CPMP SAP version 5. ECG results will be reported for the first 4-week, active-treatment period and separately for the entire 8-week study period.

6.12.7. Suicidal Ideation or Behavior

Reporting of suicidal ideation or behavior through the Columbia Suicide-Severity Rating Scale (C-SSRS) has been described in the CPMP SAP version 5. C-SSRS will additionally be reported separately for the first 4-week, active-treatment period.

6.13. Subgroup Analyses

General subgroup analyses are described in the CPMP SAP version 5.

Study BP02 will also consider the following subgroup analyses for the primary outcome.

Subgroup Variable	Categories
Neuropathic pain	Categories: Positive presence (painDETECT total score ≥19), Unclear or negative (painDETECT total score <19)

The subgroup analyses will be conducted using similar modeling approaches as the primary analysis. Additional factors in the model are described in the CPMP SAP version 5. The treatment difference at the endpoint will be reported within each level of the subgroup factor along with 95% credible intervals. Frequentist MMRM may be performed as a sensitivity analysis using the modeling approach described in the CPMP SAP version 5.

6.14. Protocol Deviations

Patients with study-important protocol deviations will be summarized by type of deviation and listed by treatment and investigative site.

Important protocol deviations for the study are described in the CPMP and BP02 Trial Issue Management Plans.

6.15. Interim Analyses and Data Monitoring

Safety review will be conducted under the auspices of an Assessment Committee (AC) according to the specifications set forth in the protocol. These analyses will be at the CPMP level and will consider data from all ongoing ISAs. Details are provided in the CPMP SAP version 5.

Interim analyses are planned for Study BP02 to be conducted when 60% of participants have completed the 4-week, active-treatment period. Details of the interim analysis can be found in the TRPA1 Statistical Analysis Center (SAC) SAP. The interim analysis will be conducted by an independent AC, and the AC will disseminate interim results, if necessary, in a manner that will not affect the conduct of the ongoing study.

6.16. Planned Exploratory Analyses

The following analyses may be conducted for exploratory purposes:

- CCI [REDACTED]

6.17. Totality of Evidence for Safety

The totality of evidence for safety analysis has been briefly described in the CPMP SAP version 5. This may be reported for any of the active-treatment period, post-active-treatment period, and entire 8-week study period. The key safety events to be considered for Study BP02 are listed below by domain:

General Adverse Event Information

- Serious adverse events related to study treatment
- Study discontinuation due to adverse event
- Treatment discontinuation due to adverse event

Cardiovascular

- QTc prolongation: >60 msec increase
- Serious cardiac disorders adverse event

Liver Function

- Hy's Law case: Serum total bilirubin (TBL) ≥ 2 Upper limit normal (ULN) and at least one of the following 2 conditions:
 - Alanine aminotransferase (ALT) ≥ 3 ULN for at least one visit
 - Aspartate aminotransferase (AST) ≥ 3 ULN for at least one visit.
- DILI (drug-induced liver injury): At least one of the following 2 conditions:

- Hy's Law
- ALT \geq 5 ULN for at least one visit.

Metabolic Function

Serious hypoglycemia adverse event

Treatment-emergent HbA1c: Shift from low/normal at baseline to high at least once.

Renal Function

Treatment-emergent abnormal eGFR: Shifts

- Mild at baseline to moderate/severe
- Moderate at baseline to severe.

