5.2. Exclusion Criteria

Participants are excluded from the study if any of the following criteria apply:

CCI [REDACTED]

[2052] Have an eGFR of less than 30 ml/min/1.73 m² based on the Chronic Kidney Disease Epidemiology Collaboration (CKD-EPI) formula at Visit 1 or Visit 2.

[2053] Women who are pregnant or breastfeeding.

CCI [REDACTED]

CCI [REDACTED]

CCI [REDACTED]

CCI [REDACTED]

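### The only renal key safety event in SAP 6.17 cannot occur in a participant whose eGFR is normal at baseline

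*SAP*

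**What the plan says.** SAP 6.17 lists the key safety events for BP02 by domain. The renal domain holds one event, treatment-emergent abnormal eGFR, defined by two shifts: "Mild at baseline to moderate/severe" and "Moderate at baseline to severe".

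The category limits are in SAP 6.12.4 (units mL/min/1.73 m²): Category 1 normal, 90 or more; Category 2 mild, 60 to 89; Category 3a moderate, 45 to 59; Category 3b moderate, 30 to 44; Category 4 severe, 15 to 29; Category 5 kidney failure, below 15 or dialysis. The same section sets the abnormality limit: "Abnormal low: <90 mL/min/1.73 m²". It also plans a fuller display: "we will summarize shift tables of eGFR changes for baseline versus postbaseline by minimum, maximum, and last observed eGFR result".

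The HbA1c event in 6.17, under Metabolic Function, is worded in the opposite direction: "Shift from low/normal at baseline to high at least once".

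Protocol 5.2 excludes candidates who "Have an eGFR of less than 30 ml/min/1.73 m²" at Visit 1 or Visit 2.

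**The concern.** A treatment-emergent abnormality is ordinarily one that was absent before treatment. Here both qualifying starting states lie below 90, so both are already abnormal by the SAP's own limit. The one group in whom an abnormal eGFR could be new, those with a normal baseline, cannot contribute an event.

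This is the only renal entry on the key safety list, in a study where 6.12.4 reports renal analytes separately from the other laboratory results. Three consequences follow if 6.17 is reported:

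- The renal entry would miss any large fall that starts from normal.
- If the denominator is all treated participants (the SAP does not state one), those with baseline 90 or more enlarge it but can never add to the numerator. The rate is diluted, and a chance imbalance between arms in the share with normal baseline would move the rates by itself.
- One report could show falls from normal to severe in the shift tables and no treatment-emergent abnormal eGFR in the totality-of-evidence summary.

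A second, conditional question is whether severe in 6.17 means Category 4 only, or Category 4 and worse. The SAP lists "Category 5: Kidney failure" as a separate category and does not name it in the 6.17 event.

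**Working it through.** The plan states no figure to reproduce. The check is to list the possible shifts and apply the 6.17 rule to each.

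**Inputs.** Category limits and the abnormal limit of 90 from SAP 6.12.4; the two qualifying shifts from SAP 6.17; baseline eGFR taken as 30 or more, from Protocol 5.2, so baseline is Category 1, 2, 3a or 3b.

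**Step 1: who can have the event.** Mild is 60 to 89 and moderate is 30 to 59. Both ranges lie wholly below 90. A normal baseline ("Category 1: Normal or increase in GFR") appears in neither shift.

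**Step 2: apply the rule.** The shifts checked are normal or mild to moderate or worse, and moderate to severe or worse.

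| Baseline → postbaseline | Severe = Category 4 only | Severe includes Category 5 |
|---|---|---|
| 1 → 3a | no | no |
| 1 → 3b | no | no |
| 1 → 4 | no | no |
| 1 → 5 | no | no |
| 2 → 3a | yes | yes |
| 2 → 3b | yes | yes |
| 2 → 4 | yes | yes |
| 2 → 5 | no | yes |
| 3a → 4 | yes | yes |
| 3a → 5 | no | yes |
| 3b → 4 | yes | yes |
| 3b → 5 | no | yes |
| **Counted** | **5 of 12** | **8 of 12** |

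The four rows that start from normal are missed in both columns. The three that change (2 → 5, 3a → 5, 3b → 5) depend on the meaning of severe. Even on the narrow reading, a participant in those rows would count if another visit fell in a listed category.

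Adding the two remaining one-step worsenings, 1 → 2 and 3a → 3b, gives 5 + 4 + 3 + 2 = 14 worsening shifts from baselines 1, 2, 3a and 3b. The rule counts 5 of 14, or 8 of 14 if severe includes Category 5; again none starts from normal.

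**Step 3: size of the falls.** Percentage fall = (baseline − postbaseline) / baseline.

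- Smallest counted fall from mild to moderate: 60 → 59, 1/60 = 1.7%.
- Smallest missed fall from normal to moderate: 90 → 59, 31/90 = 34.4%.
- Normal to severe, missed: 90 → 29, 61/90 = 67.8%.

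**The case against.** The strongest reply is that nothing is hidden. SAP 6.12.4 plans eGFR shift tables by minimum, maximum and last result, change in serum creatinine, and a summary of abnormal eGFR. A fall from 90 to 29 appears there, and would also enter 6.17 through its general adverse-event entries if it led to a related serious event or a discontinuation. SAP 6.17 says only that the summary may be reported, and in the visible text no test or stopping rule depends on it. All of this stands and limits the harm. It does not make the event definition right, and an objective laboratory event should not depend on whether an adverse event was reported.

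The counts above are counts of category cells, not of participants or probabilities. That is also true, and the set of 12 is the set a corrected rule should capture, so full coverage after correction holds by construction. The contrast between small and large falls is partly a feature of any threshold rule: with normal added as a starting category for moderate or worse, 90 to 60 (33.3%) and 59 to 30 (49.2%) would still not count. Leaving those one-category shifts out is a defensible choice for a key safety event. Leaving out a fall from normal to severe is not.

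The sponsor could instead rename the event as worsening of an already reduced eGFR. That would cure the label, but the only renal key event would still be blind to participants with normal baseline.

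The Category 5 gap rests on the narrow reading of severe. Since 6.17 merges 3a and 3b into moderate and does not cite the categories, severe or worse may well be intended. That part is a request for clarification.

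Finally, the master-protocol SAP (CPMP SAP version 5) was not available and could hold conventions on shift terms. SAP 6.17 says it describes this analysis briefly, and the BP02 list is given as study-specific, so this leaves some doubt but does not remove the point.

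**Conclusion.** The concern holds. Followed exactly, SAP 6.17 cannot record treatment-emergent abnormal eGFR in anyone with a normal baseline, whichever way severe is read. It captures 5 of the 12 relevant shifts as written and 8 of 12 on the wider reading, and misses all 4 from normal on both.

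This rests on two assumptions: that the 6.17 terms carry the 6.12.4 cut-offs, and that analysis baseline respects the entry limit of 30. The number of participants affected cannot be computed, because the documents give no baseline eGFR distribution. The point should be fixed. It affects a safety summary that may or may not be reported; the underlying data and the 6.12.4 shift tables are intact.

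**What to change.** Redefine the renal event in SAP 6.17, citing the Category 1 to 5 limits in 6.12.4, as either of:

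- normal or mild at baseline (Category 1 or 2) to moderate, severe or kidney failure (Category 3a, 3b, 4 or 5) at any postbaseline visit in the period reported;
- moderate at baseline (Category 3a or 3b) to severe or kidney failure (Category 4 or 5) at any such visit.

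This covers all 12 shifts in the table (12 of the 14 possible worsenings) and settles whether kidney failure is included. State the denominator at the same time.

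The cost is two lines of SAP text and one derived flag. The categories are already needed for the 6.12.4 shift tables, and no new data are collected.

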6.18. Annual Report Analyses

Analyses will be produced as needed for the purposes of providing periodic safety reviews to regulatory agencies (for example, Development Safety Update Reports). Data from this ISA will be combined with data from other clinical studies that investigated LY3526318. In all analyses, a combined LY arm will be created, which will include participants assigned to any dose of LY3526318 in the included studies, including LY-combination regimens.

The following data will be summarized by treatment group.

Enrollment (ongoing and completed)

Demographics (Race, ethnicity, and gender)

Exposure

- Cumulative number of subjects exposed to LY3526318
- Cumulative number of subjects exposed to LY3526318 by age
- Cumulative number of subjects exposed to LY3526318 by sex
- Cumulative number of subjects exposed to LY3526318 by race

Cumulative summary of serious AEs.

The following listings will be provided.

List of serious AEs during the reporting period

List of subjects who died

Cumulative list of subjects who discontinued due to an AE (discontinued from treatment or study)

List of subjects who discontinued due to an AE during the reporting period.

Additional analyses may be added or omitted at the time of report submission as needed.

6.19. Clinical Trial Registry Analyses

Additional analyses will be performed for the purpose of fulfilling the Clinical Trial Registry (CTR) requirements.

Analyses provided for the CTR requirements include the following:

Summary of AEs provided as a dataset that will be converted to an XML file. Both “Serious” AEs and “Other” AEs are summarized: by treatment group and by MedDRA Preferred Term.

A serious AE is an AE that is considered “Serious” whether or not it is treatment emergent.

An AE is considered in the “Other” category if it is both a TEAE and is not serious. For each “Serious” AE and “Other” AE, for each term and treatment group, the following are provided:

- the number of participants at risk of an event
- the number of participants who experienced each event term
- the number of events experienced.

Consistent with www.ClinicalTrials.gov requirements, “Other” AEs that occur in fewer than 5% of participants in every treatment group may not be included if a 5% threshold is chosen (5% is the minimum threshold).

AE reporting is consistent with other document disclosures, for example, the Clinical Study Report (CSR) and manuscripts.

7. Unblinding Plan

The general unblinding plan is described in the CPMP SAP version 5 and in the Study CPMP Blinding and Unblinding Plan version 1. Unblinding considerations specific to BP02 are provided below.

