6.1. General Considerations

The estimand for the primary clinical question of interest has been described in the CPMP SAP version 5.

Unless otherwise specified, efficacy analyses will be conducted for the first 4 weeks of the double-blind period (active-treatment phase) and separately for the entire 8-week study. A post-active-treatment population will be used for analyses of the last 4 weeks of the double-blind period (post-active-treatment phase) and will include all patients who do not discontinue at or prior to Visit 5. For treatment-emergent adverse events (TEAEs), participants in the post-active-treatment population will be analyzed according to the treatment they receive during the active-treatment phase. Adverse event (AE) analyses will be reported for the first 4 weeks of the double-blind period (active-treatment phase) and separately for the last 4 weeks of the double-blind period (post-active-treatment phase). Some AEs may be reported for the entire 8 weeks if necessary. Laboratory, electrocardiogram (ECG), and vital sign results will be reported for the active-treatment phase and separately for the entire 8-week study.

Other general considerations for analyses are described in the CPMP SAP version 5.

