6.12.2. Adverse Events

The general analysis of AEs has been described in the CPMP SAP version 5.

This ISA will report TEAEs for the first 4 weeks as well as post-treatment-emergent adverse events (PTEAEs) for the last 4 weeks of the double-blind period. For TEAEs in the first 4 weeks of the double-blind period (active-treatment phase), the baseline will be prior to first dose date.

A PTEAE is defined as an event that first occurs or worsens in severity after the active-treatment phase (after Visit 5) and on or before study discontinuation. The Medical Dictionary for

Regulatory Activities (MedDRA) Lowest Level Term (LLT) will be used in the post-treatment-emergent computation. The maximum severity for each LLT during the active-treatment period (Visits 3 to 5) will be used as a reference.

The baseline of PTEAE is from the first dosing date to Visit 5. The post-active-treatment phase (after Visit 5) will be included as postbaseline for this analysis. While unusual, it is possible to have a missing severity for events. For an event with a missing severity during the baseline period, it will be treated as “mild” in severity for determining post-active-treatment emergence. Events with a missing severity during the post-active-treatment period will be treated as “severe” and PTEAEs will be determined by comparing with the active-treatment period.

PTEAEs will be summarized by Preferred Term and by Preferred Term within System Organ Class in participants who received LY3526318.

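### The registry rule admits only non-serious TEAEs, but SAP 6.1 and 6.12.2 disagree on whether an event after Visit 5 can be a TEAE and on which arms are summarised then

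*SAP*

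**What the plan says.** **SAP 6.19 (registry).** A non-serious event is classed as *Other* if "it is both a TEAE and is not serious". A serious event is counted "whether or not it is treatment emergent". For each term and arm, the dataset gives participants at risk, participants with the event, and the number of events. No collection period is stated for either class, and PTEAEs are not mentioned. The section adds that registry AE reporting agrees with the CSR and other disclosures.

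**SAP 6.12.2 (adverse events).** AE reporting is split at Visit 5: "This ISA will report TEAEs for the first 4 weeks as well as post-treatment-emergent adverse events (PTEAEs) for the last 4 weeks". In weeks 1-4 the TEAE baseline is the time before first dose. A PTEAE is an event that first appears, or becomes more severe, after Visit 5, and its reference is different: "The baseline of PTEAE is from the first dosing date to Visit 5". On the arms to be shown: "PTEAEs will be summarized by Preferred Term and by Preferred Term within System Organ Class in participants who received LY3526318".

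**SAP 6.1 (general considerations).** "For treatment-emergent adverse events (TEAEs), participants in the post-active-treatment population will be analyzed according to the treatment they receive during the active-treatment phase". That population exists for the analysis of weeks 5-8 and takes in everyone who has not discontinued by Visit 5. The section commits to AE analyses of the last 4 weeks and permits, without requiring, reporting of some AEs over all 8 weeks.

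**Elsewhere.** The protocol's abbreviations appendix defines a TEAE by reference to a defined treatment period and gives no length. The protocol synopsis describes the double-blind treatment period as 8 weeks. SAP 6.12.2 leaves the general AE analysis to CPMP SAP version 5, which is not among the documents.

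**The concern.** Entry to the *Other* table depends on one term, and two sections of the same SAP use that term for different windows. A programmer who follows 6.12.2 and one who follows 6.1 would build different registry datasets, and nothing in 6.19 says which is intended.

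The difference falls on a period of interest. SAP 5.1 has the LY3526318 arm switch to placebo at Visit 5, so weeks 5-8 are when events after stopping the drug would appear. On the narrower reading, the public table would show serious events from that phase but not new non-serious ones. The phase's own PTEAE summary would have no placebo column against which to judge the LY3526318 events.

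**Working it through.** The plan gives no figure to reproduce. The check is to take each type of event through the two wordings.

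| Event | Following 6.12.2 | Following 6.1 |
|---|---|---|
| Non-serious, new in weeks 1-4, either arm | TEAE; in *Other* | TEAE; in *Other* |
| Non-serious, first occurs or worsens after Visit 5, LY3526318 arm | PTEAE; in the PTEAE summary; no stated route into *Other* | Can be a TEAE; in *Other* |
| Non-serious, first occurs or worsens after Visit 5, placebo arm | Meets the PTEAE definition but is outside the stated summary; no stated route into *Other* | Can be a TEAE; in *Other*; in the weeks 5-8 analysis |
| Serious, any time | In *Serious* | In *Serious* |

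Three points follow.

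1. **The affected events.** The two wordings diverge only for non-serious events that begin or worsen after Visit 5. A participant already counted for a term in weeks 1-4 stays counted on either wording. The event count for that term could still differ, because 6.19 asks for events as well as participants.

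2. **The affected follow-up.** Nominally, weeks 5-8 are 4 × 7 = 28 days and the double-blind period is 8 × 7 = 56 days, so 28/56 = 50% of planned follow-up is in question. This is calendar time. The documents give no event rates, so the share of events cannot be derived.

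3. **The baseline.** Admitting any event flagged TEAE or PTEAE would not be a clean repair, because the flags use different references. Take an event that is moderate before dosing, mild during weeks 1-4 and moderate again after Visit 5. It exceeds its maximum severity in the active-treatment period, so it is a PTEAE. It is no worse than before the first dose, so it is not treatment emergent against that baseline. Pooling the flags would put two definitions of emergence into one table.

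**The case against.** The strongest reply is that nothing in the SAP restricts TEAEs to weeks 1-4. Section 6.12.2 says what is reported in each period. Only the PTEAE is formally defined there, and the reference to TEAEs in the first 4 weeks would carry a redundant qualifier if TEAEs could occur at no other time. Section 6.1 uses the term for the weeks 5-8 population, and the protocol glossary can be read to cover the whole 8-week double-blind period. The stated consistency with the CSR also sits better with the inclusive reading, and CPMP SAP version 5 may settle the matter.

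Much of this stands. A reader might infer any of three stronger claims, and the documents do not support them:

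- **That 6.19 certainly drops all non-serious events in weeks 5-8.** The loss follows from 6.12.2 but not from 6.1.
- **That half of the events are lost.** The 50% is follow-up time under one reading.
- **That placebo events after Visit 5 are reported nowhere.** Section 6.1 promises AE analyses of the last 4 weeks in a population that includes placebo participants.

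Counting serious events without an emergence condition is also not a fault in itself.

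The reply does not remove the conflict. The glossary does not say which treatment period it means, and SAP 5.1 ends the active-treatment period at Visit 5. Reporting AEs over 8 weeks is optional in 6.1, whereas laboratory, ECG and vital-sign results are committed to it. The consistency statement names no period. SAP 6.12 says its subsections add ISA-specific considerations to the CPMP rules, and the separate PTEAE class appears there, so 6.19 should say how that class is treated whatever the CPMP document says.

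**Conclusion.** The point holds as an internal conflict with a possible consequence. Sections 6.1 and 6.12.2 disagree on the TEAE window and on the arms summarised after Visit 5, and 6.19 relies on the disputed term without stating a period. One supported reading leaves the public *Other* table without non-serious events that start or worsen after Visit 5, in both arms, and the PTEAE summary without a comparator. The other reading includes those events. At most 28 of 56 planned days are affected, and the number of events is unknown. The conclusion rests on the supplied documents alone. CPMP SAP version 5 could establish the intended TEAE window, but the wording of this SAP would still need aligning. It should be corrected because the repair is cheap and one reading makes the public AE table incomplete.

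**What to change.** - **SAP 6.19.** Define *Other* as non-serious AEs that first occur, or worsen relative to the pre-first-dose baseline, at any time in the 8-week double-blind period, in both arms. Count each participant once per Preferred Term, with all treated participants as the at-risk denominator. Using one baseline avoids pooling the TEAE and PTEAE flags.
- **SAP 6.12.2.** Summarise PTEAEs for both arms by active-phase treatment, keeping the existing PTEAE definition and its own baseline for that summary.
- **SAP 6.1 and 6.12.2.** Use TEAE in the same sense in both sections and say which window it covers.

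The cost is a few sentences in the SAP, an emergence flag over 8 weeks in the registry dataset and one added placebo column in the PTEAE tables. Reported *Other* counts would be slightly higher than under the narrower reading.
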